3.2 DRUG ADMINISTRATION

3.2.1 Cell infusion and other drug Administration

Inpatient treatment will be according to the following schedule. Cell infusions may be slowed or delayed as medically indicated. Administration of diuretics, hydration, and electrolyte monitoring and replacement will be performed as clinically indicated.

Day 0

E7 TCR cells

The E7 TCR cells $(1x10^{11} \text{ cells})$ will be delivered to the patient care unit by an authorized staff member. Prior to infusion, the cell product identity label is double-checked by two authorized staff (MD or RN) and an identification of the product and documentation of administration are entered in the patient's chart (as is done for blood banking protocols). E7 TCR T cells $(1x10^{11} \text{ cells})$ will be administered intravenously over 20 to 30 minutes via non-filtered tubing, gently agitating the bag during infusion to prevent cell clumping. A peripheral IV may be used if access is adequate (in general, two 18 gauge or larger IVs should be established). A PICC line or other central line may be used if peripheral access is not adequate.

3.3 STUDY CALENDAR

								Follow-up Period					
Procedure	Screening/ Baseline ²	Day 0	Day 1	Day 2	Day 3	Daily until d/c	1 wk (Days 5-8)	2 wk (Days 10-14)	Monthly f/u ⁷ (Month 1 is also End of Treatment Visit)	Annual Followup for 5 years after infusion			
History, physical exam, and review of systems ¹	X	\mathbf{X}^{1}	\mathbf{X}^1	\mathbf{X}^1	X ¹	X ¹	X	Х	Х				
Vital signs	X	Х	Х	Х	Х	X	X	Х	Х				
Concomitant medications	Х	Х	Х	Х	Х	Х	Х	Х	Х				
ECOG performance status	X						X	Х	Х				
Chest x-ray	X												
EKG	X												
Screening labs: HIV, HBV serology, HCV serology, thyroid panel, PT/PTT, Beta-HCG pregnancy test in women of childbearing potential, HLA-A typing for HLA-A*02:01 allele positivity	Х												
HPV-16 verification and pathology review for confirmation of diagnosis ³	Х												

							Follow-up Period				
Procedure	Screening/ Baseline ²	Day 0	Day 1	Day 2	Day 3	Daily until d/c	1 wk (Days 5-8)	2 wk (Days 10-14)	Monthly f/u ⁷ (Month 1 is also End of Treatment Visit)	Annual Followup for 5 years after infusion	
Cervical high-risk HPV testing	Х										
Cardiac stress test and/or pulmonary function tests ¹¹	Х										
Sodium (Na), Potassium (K), Chloride (Cl), Total CO2 (bicarbonate), Creatinine, Glucose, Urea nitrogen (BUN), Albumin, Calcium total, Magnesium total (Mg), Inorganic Phosphorus, Alkaline Phosphatase, ALT/GPT, AST/GOT, Total Bilirubin, Direct Bilirubin, LD, total protein, CK, uric acid, CBC with differential and TBNK	X						X	X	X		
HSIL measurements, vulvar biopsy, and photographs ⁴	Х							Х	Х		
Leukapheresis ¹²	Х							Х			
Replication Competent Retrovirus (RCR) testing ⁵	Х								X ⁵		

							Follow-up Period					
Procedure	Screening/ Baseline ²	Day 0	Day 1	Day 2	Day 3	Daily until d/c	1 wk (Days 5-8)	2 wk (Days 10-14)	Monthly f/u ⁷ (Month 1 is also End of Treatment Visit)	Annual Followup for 5 years after infusion		
Research samples: peripheral blood lymphocytes, plasma, and serum ⁶	Х		Х		Х	X^6	Х	Х	Х			
E7 TCR T cells		Х										
E7 TCR assay ¹⁰	Х		Х				Х	Х	Х			
Response Evaluation									Х			
NIH Advance Directives Form ⁸	Х											
HSIL and patient status update9										Х		
Adverse Events		Х	Х	Х	Х	Х	Х	Х	Х			

¹ Patients will have a full history and physical at screening, on admission to the hospital, and on follow-up visits. While inpatient, patients will have a daily review of systems and physical exam

²Exact timeline is indicated in Sections 2.2 and 2.4

³ Vulvar HSIL must be HPV-16+ by PCR, RNA, or in situ hybridization test from a CLIA certified laboratory prior to treatment.

⁴ Vulvar biopsies will be performed as a punch biopsy under local anesthetic in the outpatient clinic within 8 weeks prior to starting therapy, at 2-week follow-up (day 10-14), and at 1-month follow-up (day 27-34) for all patients. An additional biopsy will be obtained at the time a patient comes off-treatment (e.g. at time of progression, at time of complete response, or at 6-month visit for patients with continuing partial response). Biopsies will be performed only if technically feasible, if they do not interfere with response assessment, and if the patient provided consent. The investigators may elect not to perform biopsies at their discretion (i.e. safety concerns, patient concerns, etc.). HSIL photographs will occur at each follow up visit. HSIL measurements will occur at baseline and at each monthly follow-up visit.

⁵ Patients' blood samples will be obtained and undergo analysis for detection of replication competent retroviruses (RCR) by PCR prior to cell infusion and at approximately 3, 6, and 12 months post cell administration. Blood samples will be archived annually thereafter if all previous testing has been negative with a brief clinical history. The ETIB preclinical core staff will cryopreserve 2 vials of cells if possible. If less than 10 million cells are available, only 1 vial of cells will be cryopreserved.

⁶ Research samples will be collected pre-treatment (within four weeks prior to cell infusion); posttreatment on post-therapy day 1, post-therapy day 3, thereafter any MWF while still an inpatient for one week, and thereafter weekly while still inpatient; and post-treatment at each research visit. For each time point, six 8mL CPT tubes will be drawn (5 for PBMC and 1 for plasma) and one 8mL SST tube (for sera). Processing and storage are as described in section **5**.

⁷ All patients will follow-up at 1, 2, and 3 months after cell infusion (+/- 7 days). Patients with no response at the 3-month evaluation will be referred for standard of care therapy. Patients with a partial or complete response at the 3-month evaluation will continue to follow up at 4, 5, and 6 months for safety, response, and research evaluations (+/- 7 days). After the 6-month response assessment patients with partial response will be referred for standard of care therapy and patients with a complete response will continue to have follow-up every 3 months (+/- 30 days) for 2 visits, then every 6 months (+/- 30 days) for 2 visits (2 years of follow up total). ⁸As indicated in section 10.4, all subjects \geq age 18 will be offered the opportunity to complete an NIH advanced directives form. This should be done preferably at baseline but can be done at any time during the study as long as the capacity to do so is retained. The completion of the form is strongly recommended, but is not required.

⁹Subjects or local treating physician will be contacted to collect information annually for five years after the date of cell infusion:1) procedures or treatments for vulvar HSIL, 2) procedures or treatments for cervical, vaginal, or anal intraepithelial neoplasia, 3) occurrence of vulvar, cervical, or anal cancer. This followup can be conducted via telephone.

¹⁰Clinical assay may be performed at these time points by the NCI Flow Cytometry Laboratory in the Laboratory of Pathology.

¹¹If applicable, see section 2.1.2.6.

¹²Except for patients previously treated on protocol 17-C-0116.

3.4 POTENTIAL REPEAT TREATMENT

Patients may be retreated if an E7 T cell product can be generated from cells collected prior to any T cell gene therapy treatment. Patients eligible for retreatment include those who had partial or complete response to E7 TCR T cell therapy that subsequently progress. Patients must meet the original eligibility criteria to be considered for retreatment. Research assessments will be performed at the same time intervals used for initial treatment. Patients who develop grade 3 or 4 toxicity due to cell infusion will not be retreated. A maximum of 1 retreatment course may occur. The second treatment will not begin until at least 12 weeks after initial T cell therapy but must be within 5 years from the date of progressive disease.

Note: Response data for all treatments will be captured in the database however only the response data from the first treatment with E7 TCR T cells will be used in determination of response.

3.5 **ON-STUDY EVALUATIONS**

Please see the study calendar in Section 3.3 for details regarding on-study evaluations.

3.5.1 Long-term Follow-Up:

Long-term follow-up of patients receiving gene transfer is required by the FDA and must continue even after the patient comes off the study. Long-term follow-up will be done under a different long-term gene therapy follow-up protocol (20C0051).

3.6 CRITERIA FOR REMOVAL FROM PROTOCOL THERAPY AND OFF STUDY CRITERIA

Prior to removal from study, effort must be made to have all subjects complete a safety visit approximately 30 days following the last dose of study therapy.

3.6.1 Criteria for removal from protocol therapy

Note: Subjects removed from protocol therapy may still be eligible for up to one course of retreatment per section **3.4**. The same off treatment criteria apply after the second potential course as for the first. Data collection and assessments required while off therapy are addressed in sections **6.1** and **3.3** respectively.

- Completion of protocol therapy
- Positive pregnancy test
- Progression of disease
- Participant requests to be withdrawn from active therapy
- Investigator discretion
- Unacceptable toxicity

3.6.2 Off-Study Criteria

- Screen failure
- Completed study follow-up period

- Inability to generate a cell product. A second attempt may be made to generate a cell product from the patient. If the second attempt fails, that patient will be removed from the study and replaced with another patient.
- Participant requests to be withdrawn from study
- There is significant noncompliance
- The investigators decide to end the study
- The investigators decide it is in the patient's best interest
- Death

4 CONCOMITANT MEDICATIONS/MEASURES

4.1 **PROHIBITED MEDICATIONS**

Patients needing systemic steroid therapy greater than the equivalent of 5 mg of prednisone may not participate in this study.

4.2 BLOOD PRODUCT SUPPORT

Patients are unlikely to require blood product support as a side effect of therapy. However, any patient on study may receive platelets and packed red blood cells (PRBC's) in clinically needed. As a general guideline, patients may be transfused for:

- Hemoglobin < 8 gm/dl
- Platelets $< 10,000/\text{mm}^3$

All blood products will be irradiated and leukocyte filters will be utilized to decrease sensitization to transfused WBC's.

4.3 OTHER CONCOMITANT MEDICATIONS/MEASURES

Concomitant medications to control side effects of therapy may be given. Meperidine (25-50 mg) will be given intravenously if severe chilling develops. Other supportive therapy will be given as required and may include acetaminophen (650 mg q4h), indomethacin (50-75 mg q8h) and ranitidine (150 mg g12h). If patients require steroid therapy they will be taken off treatment. Patients who require transfusions will receive irradiated blood products. Ondansetron will be administered per standard dosing instructions as needed for nausea and vomiting. Additional antiemetics will be administered as needed for nausea and vomiting uncontrolled by ondansetron.

5 BIOSPECIMEN COLLECTION

5.1 CORRELATIVE STUDIES FOR RESEARCH

The amount of blood that may be drawn from adult patients for research purposes shall not exceed 10.5 mL/kg or 550mL; whichever is smaller, over any 8-week period.

5.1.1 Pre cell infusion evaluations

• The following samples may be drawn for research and sent to the ETIB preclinical core within 4 weeks prior to cell infusion. Send to Pre-Clinical Core lab; Attention [name], [name] contact [contact].

- 6 CPT tubes (8mL each). One CPT tube per time point may be used to collect 4mL of plasma, which may be frozen in 4mL vials. PBMC from the remainder of the CPT tubes may be frozen in aliquots of 10 x 106 cells/vial
- 1 SST tube (8mL) for sera. Serum will be processed in the ETIB Pre-Clinical Core and aliquoted into vials of 0.5-1 mL each.
- 5.1.2 Post cell infusion evaluations
 - The following samples may be drawn for research and sent to the ETIB preclinical core While the patient is inpatient, samples may be drawn on post-treatment day 1, posttreatment day 3, thereafter every Monday/Wednesday/Friday x5 days, and then weekly until discharge. Samples may also be collected at each outpatient follow-up visit. Send to Pre-Clinical Core lab; Attention [name], [name] contact [contact].
 - 6 CPT tubes (8mL each). One CPT tube per time point may be used to collect 4mL of plasma, which will be frozen in 4mL vials. PBMC from the remainder of the CPT tubes may be frozen in aliquots of 10 x 10⁶ cells/vial
 - 1 SST tube (8mL) for sera. Serum will be processed in the ETIB Pre-Clinical Core and aliquoted into vials of 0.5-1 mL each.
- 5.1.3 Optional vulvar Biopsies
 - Biopsies for research purposes will be obtained at baseline (within 8 weeks of starting treatment), 10 to 14 days after treatment, 27 to 34 days after treatment, and at the time the patient comes off-treatment (i.e. attains a complete response, experiences progression, or reaches the 6-month time point without a complete response). This biopsy schedule may be repeated for patients receiving retreatment. Clinically indicated biopsies may be obtained at any time by PI discretion if there is concern for invasive cancer.
 - Biopsies for research will be performed with a standard punch biopsy instrument of up to 4 mm diameter. At each time point, up to 3 biopsies of HSIL lesions and up to 2 biopsies of adjacent normal tissue will be performed. A formalin-fixed paraffin embedded specimen will be transported to the NCI Laboratory of Pathology for review and archiving. The contact will be [name], [name], contact [contact]. Specimens will then be transported to the ETIB preclinical core for further processing and storage. They will be delivered to Pre-Clinical Core lab; Attention [name], [name] contact [contact].
 - Processing of biopsies will depend upon the amount of tissue obtained. Examples of processing may include OTC blocks, formalin-fixed paraffin embedding, snap freezing, placing in RNAlater or other required laboratory processing technique.
 - Biopsies will not be performed if they are not technically feasible, if they will interfere with response assessment, or if a patient declines consent.
 - Samples will be stored for this protocol. Some of these samples may be archived and analyzed under another protocol 16-C-0061 (ETIB Tissue Procurement Protocol) if the subject also coenrolled on that study.
- 5.1.4 Mandatory vulvar biopsies

- Biopsies of vulvar lesions for clinical purposes will be obtained within 8 weeks prior to starting treatment if clinically indicated to rule out invasive cancer. Biopsies will be performed in the outpatient clinic under local anesthetic.
- 5.1.4 Immunological Testing
 - Leukapheresis will be performed prior to treatment (expect for patients previously treated on protocol 17-C-0116) and 10-14 days after treatment.
 - Processing of leukapheresis will be in the Department of Transfusion Medicine (DTM). Cell product may be frozen in 10 vials at concentration 100 x 10⁶ cells/mL and additional vials at 300 x 10⁶ cells/mL. Cells will be stored in a -80 degrees Celsius freezer in DTM overnight and transferred to the ETIB Preclinical Core the following day. Samples will be sent to Pre-Clinical Core lab; Attention [name], [name]. Contact [contact].
 - At other time points, peripheral blood lymphocytes (PBL) and plasma may be obtained from whole blood by purification using centrifugation. These samples will be transferred directly to the ETIB Pre-Clinical Core lab for processing. Plasma may be frozen in 4mL vials. PBL may be frozen in aliquots of 10 x 10⁶ cells/vial.
 - The following tests may be used to evaluate immunologic correlates: specific lysis and cytokine release, intracellular FACS of cytokine production, ELISPOT assays, engraftment of E7 TCR T cells and lymphocyte subset analysis.
 - Samples of all infused cell products will be cryopreserved, and retrospective analysis of infused cell phenotype and function may be performed including functionality measured by cytokine release in co-culture assays (ELISPOT, ELISA), cytotoxicity measured by cell impedance assay and characterization of T cell subsets by surface marker expression detected by flow cytometry and/or RNA sequencing.
 - Peripheral blood lymphocytes (PBL) may be tested by cytolysis assays, cytokine release and limiting dilution analysis.Immunological monitoring may consist of quantifying T cells reactive with tumor cells using established techniques such as intracellular FACS, cytokine release assays, and ELISPOT assays. Immunological assays may be standardized by the inclusion of 1) pre-infusion PBMC and 2) an aliquot of the T cells cryopreserved at the time of infusion.
 - Blood and tissue specimens collected in the course of this research project will be stored for this protocol and may be used in the future to investigate new scientific questions related to this study. If the patient is coenrolled on protocol 16-C-0061 (ETIB Tissue Procurement Protocol) their blood and tissue speciments may be used on that protocol as well.

Test/assay	Volume blood (approx)	Type of tube	Collection point (+/- 48hrs)	Location of specimen analysis		
Plasma/PBMC	48 mL	СРТ	<4 weeks prior to cell infusion	Pre-Clinical core lab (PDCMF) ([name])		

5.2 SUMMARY OF SAMPLE COLLECTION

Abbreviated Title: Immunotherapy for vulvar HSIL
Version Date: 4/27/2020

Serum	8 mL	SST	<4 weeks prior to cell infusion	Pre-Clinical core lab (PDCMF) ([name])
Plasma/PBMC	48 mL	СРТ	Post cell infusion day 1, 3, every Mon/Wed/Fri x 5 days, weekly until discharge	Pre-Clinical core lab (PDCMF) ([name])
Serum	8mL	SST	Post treatment days 1 & 3, then every Mon/Wed/Fri x 5 days, then weekly until discharge	Pre-Clinical core lab (PDCMF) ([name])
Vulvar Biopsy	N/A	N/A	< 8 weeks prior to treatment, 10-14 days after treatment, 27-34 days after treatment, and when patient comes off treatment.	Processed in [name] Lab, then transported to Pre-Clinical core lab (PDCMF) ([name])

5.3 GENE-THERAPY-SPECIFIC FOLLOW-UP

• Patients will be enrolled on the Long Term Followup Gene Therapy Study in order to collect information to meet current FDA requirements. All followup as required by the FDA will occur via the 20C0051 protocol.

5.4 SAMPLE STORAGE, TRACKING AND DISPOSITION

- 5.4.1 Storage/Tracking in the Preclinical Development and Clinical Monitoring Facility (PDCMF)
 - Samples will be ordered in CRIS and tracked through the Clinical Trial Data Management System. Should a CRIS screen not be available, the CRIS downtime procedures will be followed. Samples will not be sent outside the NIH without appropriate approvals and/or agreements, if required.
 - Patient blood and tissue samples, collected for the purpose of research under IRB approved protocols of the Experimental Transplantation and Immunotherapy Branch (ETIB), may be archived by the ETIB Preclinical Development and Clinical Monitoring Facility (PDCMF). All data associated with archived clinical research samples is entered into LabMatrix. Access is limited to PDCMF staff and ETIB clinical staff, requiring individual login and password. All staff in the PDCMF laboratory receive annually updated NIH/CIT training and maintain standards of computer security.
 - The data recorded for each sample includes the patient ID, trial name/protocol number, date drawn, treatment cycle/post-transplant time point, cell source (e.g. peripheral blood, marrow,) as well as box and freezer location. Patient demographics that correlate treatment outcomes and therapies with the samples can be obtained only through the

NCI/ETIB clinical records. As of January 2007, all newly received samples receive a unique bar code number, which is included in the sample record in the PDCMF database. Only this bar code is recorded on the sample vial and the vials will not be traceable back to patients without authorized access to the PDCMF database. All non-coded samples previously archived will be stripped of identifiers prior to distribution for any use other than as a primary objective of the protocol under which they were collected.

• Samples are stored in freezers. All samples will be labeled solely with a bar code (which includes the date, and serially determined individual sample identifier). The key will be available to a restricted number of ETIB investigators and associate investigators on the protocol. Coded samples will be stored frozen at -20°, -80° or liquid nitrogen vapor phase to -180 C according to the stability requirements in a single location under the restricted control of the PDCM Facility of ETIB.

These freezers are located onsite at the Preclinical Service laboratory (12C216) (-85° freezer) or in ETIB common equipment space (CRC/3-3273). Access to samples from a protocol for research purposes will be by permission of the Principal Investigator of that protocol in order to be used (1) for research purposes associated with protocol objectives for which the samples were collected, or (2) for a new research activity following submission and IRB approval of a new protocol and consent, or (3) for use only as unlinked or coded samples under the OHSRP Exemption Form guidelines stipulating that the activity is exempt from IRB review. Unused samples must be returned to the PDCMF laboratory. Samples, and associated data, will be stored permanently unless the patient withdraws consent. If researchers have samples remaining once they have completed all studies associated with the protocol, they must be returned to the PDCMF laboratory.

5.4.2 Storage/Track in the [name] lab

Blood, plasma, serum, and tissue samples will be processed, labeled, and stored in the ETIB Pre-Clinical Core. Samples will be requested and transferred to [name] lab as needed for analysis. The contact will be [name], [name], [contact]

Once received, the samples will be coded utilizing LabMatrix. The bar-coded samples will be stored at -80°C or in liquid nitrogen until time of use. Any unused samples will be returned to the PDCMF laboratory at the completion of all studies associated with the protocol.

Samples transferred to the [name] laboratory will be barcoded and tracked with LabMatrix.

Laboratory research data will be stored on the NCI secure server in the [name] laboratory folder with secure access by laboratory personnel only. Access to personally identifiable information (PII) is limited to the PI and study personnel who interact directly with the patient and their samples

5.4.3 Protocol Completion/Sample Destruction

• Once research objectives for the protocol are achieved, researchers can request access to remaining samples, providing they have both approval of the Principal Investigator of the original protocol under which the samples or data were collected and either an IRB

approved protocol and patient consent or an OHSRP exemption indicating that the activity is exempt from IRB review.

- The PDCMF staff will report to the Principal Investigators any destroyed samples, if samples become unsalvageable because of environmental factors (ex. broken freezer or lack of dry ice in a shipping container), lost in transit between facilities or misplaced by a researcher.
- The PI will record any loss or unanticipated destruction of samples as a deviation. Reporting will be per the requirements of section 7.2.

6 DATA COLLECTION AND EVALUATION

6.1 DATA COLLECTION

The PI will be responsible for overseeing entry of data into an in-house password protected electronic system (C3D) and ensuring data accuracy, consistency and timeliness. The principal investigator, associate investigators/research nurses and/or a contracted data manager will assist with the data management efforts. All data obtained during the conduct of the protocol will be kept in secure network drives or in approved alternative sites that comply with NIH security standards. Primary and final analyzed data will have identifiers so that research data can be attributed to an individual human subject participant.

All adverse events, including clinically significant abnormal findings on laboratory evaluations, regardless of severity, will be followed until return to baseline or stabilization of event.

Document AEs from the first study intervention, Study Day 0 through 28 days after removal from the study treatment, or until off-study, or until they initiate a new treatment, whichever comes first. Beyond 28 days after the last intervention, or initiation of new treatment as applicable, only adverse events and serious adverse events that are at least possibly related to E7 TCR T cells will be recorded. Grade 1 adverse events will not be recorded.

An abnormal laboratory value will be recorded in the database as an AE **only** if the laboratory abnormality is characterized by any of the following:

- Results in discontinuation from the study
- Is associated with clinical signs or symptoms
- Requires treatment or any other therapeutic intervention
- Is associated with death or another serious adverse event, including hospitalization.
- Is judged by the Investigator to be of significant clinical impact
- If any abnormal laboratory result is considered clinically significant, the investigator will provide details about the action taken with respect to the test drug and about the patient's outcome.

End of study procedures: Data will be stored according to HHS, FDA regulations and NIH Intramural Records Retention Schedule as applicable.

Loss or destruction of data: Should we become aware that a major breach in our plan to protect subject confidentiality and trial data has occurred, this will be reported expeditiously per requirements in section 7.2.1.

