3.1.5 Safety Protocol Stopping Rules

The study will be halted (immediately stop accrual and treatment) if any of the following safety conditions are met and we will promptly investigate and submit an amendment to the IRB and FDA if necessary:

- 1. If one or more deaths (other than death related to progressive disease) occurs within 30 days of E7 TCR T cells.
- 2. If 2 of the first 6 patients or the fraction of patients > 33% after the initial 6 patients develop grade 4 or greater adverse events (except lymphocyte count increased) possibly related to E7 TCR Tcells.

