10.2.4 Safety Analyses

If two of the first six patients develop any grade 4 event related to E7 TCR T cells or grade 3 events (except lymphocyte count increased) that does not resolve to a grade 2 or less in 48 hours or the fraction of participants with these events is greater than or equal to 33% after the initial 6 patients, then no further patients will be accrued as soon as this has been determined. Accrual may resume after appropriate treatment revision is described in approved amendment. All treatment courses with E7 TCR T cells will be considered in this analysis.

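### Section 6.1 sets no grade criterion for recording laboratory abnormalities as adverse events, so some values at grades that the safety stopping rules count can be missing from the count

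*Combined protocol and SAP*

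**What the plan says.** **Recording (6.1).** The protocol says that "An abnormal laboratory value will be recorded in the database as an AE" only if at least one listed condition applies:

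- it leads to discontinuation from the study;
- it comes with clinical signs or symptoms;
- "Requires treatment or any other therapeutic intervention";
- it is associated with death or another serious adverse event;
- "Is judged by the Investigator to be of significant clinical impact".

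A sixth bullet is an instruction on what to report once a result is considered clinically significant. The only recording rule in 6.1 that uses grade works at the bottom of the scale: "Grade 1 adverse events will not be recorded".

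**Stopping rule in 3.1.5.** Accrual and treatment halt if 2 of the first 6 patients, or later more than 33%, "develop grade 4 or greater adverse events (except lymphocyte count increased) possibly related to E7 TCR Tcells".

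**Stopping rule in 10.2.4.** The first limb, which stops accrual, concerns the highest grade: "If two of the first six patients develop any grade 4 event related to E7 TCR T cells". A second limb, for the same early patients, brings in certain toxicity one grade lower, namely "grade 3 events (except lymphocyte count increased) that does not resolve to a grade 2 or less in 48 hours". Later in accrual the trigger becomes a proportion, and it is met when "the fraction of participants with these events is greater than or equal to 33% after the initial 6 patients".

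**Reporting (10.2.3).** Toxicities are to be reported by type and grade. Safety is the trial's only secondary objective (1.1.2).

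**The concern.** The stopping rules select events by CTCAE grade, while the recording rule selects laboratory values by clinical consequence or judgement. Both stopping rules name a laboratory term, lymphocyte count increased, as an exception. That exception would serve little purpose unless other laboratory events could count.

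A value can therefore reach a grade that the rules count and still not be entered as an adverse event. Relatedness is assessed for adverse events (8.1.5, 8.2). Relatedness is also a condition of the count in 3.1.5 and, at least for grade 4, in 10.2.4. A value that is never entered has no required relatedness assessment and no stated route into the numerator.

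The trial treats at most 16 patients and its first trigger is 2 of 6, so a single unrecorded patient can decide whether the study halts. The toxicity report could be understated in the same way.

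**Working it through.** **Step 1. Which values escape.** Setting the recording criteria beside the counting criteria:

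| Laboratory value, related to treatment | Recorded under 6.1? | Counted by 3.1.5? | Counted by 10.2.4? |
|---|---|---|---|
| Grade 4, symptomatic, treated, or judged significant | Yes | Yes | Yes |
| Grade 4, meeting no 6.1 criterion | Not required | In scope by grade | In scope by grade |
| Grade 3, unresolved at 48 hours, meeting no 6.1 criterion | Not required | No | In scope by grade |
| Grade 3, resolved to grade 2 or less in 48 hours | Depends on 6.1 criteria | No | No |

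The gap is the second row for both rules and the third row for 10.2.4 only.

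**Step 2. Whether another section closes it.**

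- Section 8.1.1 defines an adverse event broadly enough to include an abnormal laboratory finding, but 6.1 then limits which laboratory values are entered.
- Section 8.2 refers back to 6.1 for the timeframe of recording.
- Sections 7.5.1 (weekly team meeting and review by the principal investigator), 7.5.2 (safety committee review, about annual) and 9 (monitoring) provide oversight. None says that the stopping rules are applied to graded laboratory data rather than to recorded events.

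**Step 3. Illustration of size.** The plan gives no operating characteristic for either stopping rule, so there is no figure of its own to reproduce. Inputs:

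- From the plan: a trigger of at least 2 of the first 6 patients.
- Assumed: true rate p of patients with a qualifying event; share u of qualifying events unrecorded, with one qualifying event per patient.

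The recorded rate is q = p(1 − u), and

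P(at least 2 of 6) = 1 − (1 − q)^6 − 6q(1 − q)^5.

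At p = 0.33:

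- u = 0: q = 0.33; 1 − 0.0905 − 0.2673 = 0.642
- u = 0.10: q = 0.297; 1 − 0.1207 − 0.3060 = 0.573
- u = 0.25: q = 0.2475; 1 − 0.1816 − 0.3583 = 0.460
- u = 0.50: q = 0.165; 1 − 0.3389 − 0.4019 = 0.259

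The same formula at other assumed rates:

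| True rate p | u = 0 | u = 0.10 | u = 0.25 | u = 0.50 |
|---|---|---|---|---|
| 0.20 | 0.345 | 0.296 | 0.224 | 0.114 |
| 0.33 | 0.642 | 0.573 | 0.460 | 0.259 |
| 0.50 | 0.891 | 0.836 | 0.726 | 0.466 |

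**Step 4. Through patient 16.** Applying the continuing 33% criterion after each patient from the seventh on, at p = 0.33, the chance of a stop by patient 16 is 0.780 with u = 0, 0.567 with u = 0.25 and 0.310 with u = 0.50. The two threshold wordings (more than 33%, and at least 33%) give the same results up to 16 patients.

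**The case against.** **The sections can be read together.** Section 3.1.5 counts adverse events and 6.1 says which laboratory values become adverse events, so there is no outright contradiction. That is fair. That other laboratory events were meant to count is an inference from the named exemption. Even so, the plan never says that a value at a counted grade may be left out because it was untreated and not judged significant.

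**Asymptomatic values are not excluded as a class.** A reader might infer that 6.1 drops all of them. It does not: an asymptomatic value is recorded if it is treated, leads to discontinuation, accompanies a serious event or is judged significant. Many investigators would judge a grade 4 value significant.

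**The grades differ between the rules.** A reader might also infer that both rules lose grade 3 and grade 4 values. Section 3.1.5 counts no grade 3 events, and 10.2.4 counts grade 3 only when it has not resolved to grade 2 or less in 48 hours.

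**Judgement remains in any case.** Relatedness is itself an investigator's assessment, so full recording would not make the count a matter of grade alone. It would ensure that the assessment is made.

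**A large hidden share is not shown.** No conditioning or aldesleukin is given, and 4.2 calls a need for blood product support unlikely. A patient with another recorded qualifying event still counts, so the calculation overstates the loss where patients have several. The oversight in 7.5 and 9 also makes a missed related grade 4 value less likely. These points bear on size. They do not close the gap.

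**Conclusion.** The concern holds in a limited form. Under the plan as written, a grade 4 laboratory value, or under 10.2.4 an unresolved grade 3 value, that meets none of the 6.1 criteria need not be recorded or assessed for relatedness. It can then be missing from the stopping counts and from the report of toxicities by type and grade. The direction is certain, because the filter can only lower the count.

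The size is not known. The event rate and the unrecorded share are assumptions, and at a true rate of 33% the loss in the chance of counting 2 of the first 6 runs from 7 percentage points (10% unrecorded) to 38 (50% unrecorded). The documents do not support naming one of these as the expected loss.

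The primary endpoint and its two-stage design are not affected. This is a cheap improvement that should be made.

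**What to change.** Add one sentence to 6.1: any laboratory value at a CTCAE grade counted by the stopping rules, other than lymphocyte count increased, is recorded as an adverse event with a relatedness assessment, whether or not it is symptomatic or treated.

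Sections 3.1.5, 6.1 and 10.2.4 must be reconciled, since the two stopping rules count different grades and 10.2.4 attaches the lymphocyte exemption to its grade 3 part. The recording sentence should follow whichever grades and exemptions the reconciled rule uses. This point takes no position on which those should be.

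**Cost.** A few more adverse event entries in at most 16 treated patients, and a slightly higher reported rate of grade 3 and 4 events. Recording a grade needs no new test, because chemistry and blood counts are already scheduled at baseline, 1 week, 2 weeks and the monthly visits (3.3). That row of the calendar has no mark on days 0 to 3 or daily until discharge. The scheduled tests therefore cannot by themselves show whether a grade 3 value resolved within 48 hours, and the reconciled text should say how that part of 10.2.4 is to be established.
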